- Children participate in the BGCAA's after-school program with CATCH curriculum as well as other activities (such as active recreational time, homework/power hour, and snack time)—as described for Arm #1.
- Children participate in daily (M-F) recreational time (45-60 min) which consists of a mixture of free play, structured physical activity games, and/or sports activities (including soccer, football, and basketball).

- They will be attending the same sites as the intervention arm (Arm #1). Hence, they will be exposed to the same after-school content at each participating site.
- The after-school program happens immediately after school and BGCAA provides transportation from the school to offsite locations if the program is not held at child's school.
- At the end of the study, the reference parent will receive \$120 as HEB grocery store gift cards, independently of their end-point measurement being obtained.

SUBJECT POPULATION

12 Protected Subject Populations

Click on the check box (or double click and type an "X" if using Google Docs) each population, if they are specifically studied for this research.

 Active Military Personnel	 Children/Minors	 Decisionally Impaired Adults
 Emancipated Minors	 Fetuses	 Individuals with Limited English Proficiency
 Neonates (Uncertain Viability)	 Neonates (Non-Viable)	 Prisoners
 Pregnant Women	 UT Staff/Employees	 UT Students

13 Research Participant Information

Describe the general characteristics of the subject populations or groups including gender, health status, and any other relevant characteristics. **If you have multiple research populations (e.g., teachers and students), clearly outline characteristics for each group.**

A household will be the subject of randomization, one index parent/caregiver and one index child (parent-child dyads) who meet inclusion criteria will be invited to participate in the research activities (data collection).

Participation in the BGCAA after-school program is governed by that organization according to their mandate.

b Minimum Age

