We will invite all families across all 11 participating sites. Given numbers from the current year, we expect total number that could be invited (meeting inclusion/ exclusion criteria) to be 350 total index parent and child pairings. Below we discuss various realistic recruitment and retention scenarios given the capacity of our partner, BGCAA. Our aim will be to maximize recruitment but are prepared for various recruitment scenarios.

15 Sample size rationale

Describe your sample size rational below.

We are conducting both as-treated (AT) and intention-to-treat (ITT) analyses.

To inform our sample size calculations and power for the ITT and AT analyses, we relied on information from the pilot trial conducted at BGCAA sites in the spring of 2021. The pilot also used the SPAN tool to measure diet for child and caregiver (Kahlon et al., 2022).

For the AT analysis, we use the results of the pilot from Spring of 2021 showing a dose response correlation, which was $r = 0.31$. We have 80% power to detect this association with total $N = 79$. Even if the enrollment and retention is as low as $n = 64$ for each active arm, we would be able to detect a dose-response correlation as low as 0.24 in the AT framework.

From the 2021 study, the effect size for the overall child's HEI (Healthy Eating Index) at the end of the study was .47 with an ICC of .20 for person x site clusters. For the present study, to be able to detect an identical difference between the two randomized arms (Program+Family Support and After-school program only) with 80% power at $\alpha = .05$, we would need to retain 120 children in each arm. Considering a 15% attrition rate, a target recruitment of approx. 140 children into each active arm would permit sufficient power to observe the targeted moderate group difference.

Given the recruitment pool for our sample is limited by the BGCAA program capacity, we estimated the changes in effect sizes (i.e., our ability to detect differences) in two scenarios, maintaining 80% power at $\alpha = .05$.

Assuming that all eligible households will be invited to participate and that a conservative potential pool of approx. **300 households** will be maintained in the fall (in the current school semester, Boys and Girls Club has approximately 313 households attending their after-school program with at least one child), we can expect the following:

- If we successfully enroll 75% in the study, N=226

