 - With n=113 households in each active arm, we can detect a moderate effect size $d = .45$.
 - Considering 15% attrition in each arm, we would end the study with n=96 in each active arm and able to detect an effect size of $d = .49$.
- If we successfully enroll 50%, N=150
 - With n=75 in each active arm, we can detect a difference of moderate effect size $d = .55$.
 - Considering 15% attrition, n=64 in each arm enable us to detect an effect size of $d = .60$.

Therefore, we will invite to participate in the study all households with at least one eligible child to maximize our ability to detect meaningful mean differences in children's HEI between the two active arms.

SCREENING AND RECRUITMENT

16

Identification and Screening

*Check the box below if this study involves a screening process **prior** to the informed consent process.*

This study involves obtaining information or biospecimens for the purpose of screening, recruiting or determining eligibility of prospective subjects prior to informed consent by either:

- 1. Oral or written communication with the prospective subject or LAR**
- 2. By accessing records containing identifiable private information or stored identifiable biospecimens.**

17

Identification and/or Screening Procedures

Describe the identification and/or screening procedures below.

The Identification of interested families will be done both by the BGCAA staff and our study staff through the various places where BGCAA can be reached, as follows:

- Distribution of flyers containing a QR code that links to an interest form to request more information later – at BGCAA sites & digitally via Class Dojo app that BGCAA staff use to communicate with families. In this form, if collecting interest information, we will collect the parent/guardian name, child name, school and/or afterschool site they attend, contact phone number, grade child will be in the fall, and preferred language. The path the QR code takes

them will be to a secure and HIPAA-compliant database (UT Box, REDCap, and/or UT Qualtrics) that will securely house the information to be filled out by the parent/guardian.

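### Section 15's ITT sample size (120 per arm) and its four detectable effects do not follow from the stated inputs or from one another, and the plan does not say what the ICC of .20 measures or how it was used

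*Combined protocol and SAP*

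**What the plan says.** **Planning figures (Section 15, Sample size rationale).** The 2021 pilot effect on child HEI "was .47 with an ICC of .20 for person x site clusters". To detect the same difference with 80% power at alpha .05, the plan says "we would need to retain 120 children in each arm". Allowing for 15% attrition, this becomes about 140 recruited per arm. Two enrolment scenarios follow, at the same power and alpha. The first begins "With n=113 households in each active arm, we can detect a moderate effect size" of .45, falling to 96 per arm and .49 after attrition. The second has 75 per arm and .55, then 64 per arm and .60. Section 15 gives no formula, design effect or cluster size, and does not say whether the test is two-sided.

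**Design and model.** Sections 4 and 13 randomise households 1:1, with one index child each, stratified by SNAP status. Section 11 says of the control children: "They will be attending the same sites as the intervention arm (Arm #1"). Section 14 gives 11 sites. Section 5 fits mixed models with random intercepts to baseline, mid-point and end-point data, adjusts for site clustering, and names time by treatment among its target terms.

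**The concern.** The required size is far above what an effect of .47 needs in an ordinary two-arm comparison, and the ICC is the only reason on offer. In this trial both arms are present at each site. A between-site ICC therefore does not raise the variance of the arm difference, and adjusting for site lowers it. The required size and the scenario rows also appear to carry different inflations.

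Section 15 is the only power justification for the ITT comparison. It tells the reader that neither retention scenario (96 or 64 per arm) can detect the pilot effect with 80% power. Whether that is true depends on a quantity the plan does not define.

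**Working it through.** **Inputs.** d = .47, ICC = .20, 80% power, alpha .05, 120 per arm, 15% attrition and the four n and d pairs, all from Section 15; 11 sites from Section 14. Assumed here: a two-sided t-test and, except for the change contrast in step 5, a comparison of means at one time point.

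**1. The plan's 120.** For d = .47 the t-test solution is n = 72.04, so 73 per arm. The ratio 120/72.04 = 1.67 is the variance factor that 120 implies. With no inflation, 120 per arm has about 95% power. The step to about 140 is consistent with 120 (120/.85 = 141.2; 120 × 1.15 = 138).

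**2. The four rows.** The plain detectable d is solved from the same t-test at each n.

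| n per arm | plain d | stated d | stated/plain | variance factor |
|---|---|---|---|---|
| 113 | .374 | .45 | 1.20 | 1.45 |
| 96 | .406 | .49 | 1.21 | 1.45 |
| 75 | .460 | .55 | 1.19 | 1.43 |
| 64 | .499 | .60 | 1.20 | 1.45 |

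Multiplying plain d by 1.20 gives .449, .488, .553 and .599, which round to all four stated values. The number 1.20 equals 1 + ICC, but here it multiplies d, so the variance factor is 1.44. That is a numerical match and does not show the method used.

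**3. Required size against rows.** At fixed power, n is close to proportional to 1/d². Each row therefore implies an n for .47:

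- 113 × (.45/.47)² = 103.6
- 96 × (.49/.47)² = 104.3
- 75 × (.55/.47)² = 102.7
- 64 × (.60/.47)² = 104.3

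From the variance factor, 72.04 × 1.44 = 103.7. Rounding does not close the gap to 120. Taking each stated d at its upper rounding limit and .47 as .465, the largest result is 96 × (.495/.465)² = 108.8. This step needs no view on what the ICC means.

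**4. A site-randomised design effect.** This is 1 + (m − 1) × .20, where m is children per site. For 240 children, m = 21.8 and the factor is 5.16. For the four rows (m = 20.5, 17.5, 13.6, 11.6) it is 4.91, 4.29, 3.53 and 3.13. Neither 1.67 nor 1.44 is in this range, and the stated rows do not vary with m.

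**5. What the inputs give on each reading of .20.**

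*Between-site ICC.* If d is in within-site SD units, 73 per arm. If d is in total-SD units with site in the model, the variance factor is 1 − .20 = .80 and n = 57.8, so 58. Power at .47 is 90% to 95% with 96 per arm and 75% to 84% with 64. A simulation on the total-SD scale (11 sites, households individually randomised, no treatment-by-site variation) gave, with site adjustment, 76% at 58 per arm, 81% at 64 and 94% at 96. The lower end of 58 is thus slightly optimistic once 11 site effects are fitted.

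*Within-child correlation, change contrast.* Baseline to end-point change has variance factor 2 × (1 − .20) = 1.60. A linear slope over 0, 6.5 and 19 weeks (assumed visit times), scaled to the full period, has factor .80/.517 = 1.55. The t-test solutions are 111.1 and 114.7. Power at .47 is 82% to 83% with 120 per arm, 73% to 74% with 96 and 55% to 56% with 64.

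*Within-child correlation, baseline-adjusted end-point.* The factor is 1 − .20² = .96, giving n = 69.2, so 70.

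None of these variance factors (.80, .96, 1.00, 1.55 to 1.60) equals 1.67 or 1.43 to 1.45.

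**The case against.** The strongest defence is that the label attached to the ICC joins person and site, so .20 need not be a site ICC. Section 5 fits random intercepts to three repeated measures and tests time by treatment, which makes a within-child component plausible. On that reading a change contrast needs about 111 to 115 per arm, within about 4% to 8% of 120. The stated size is then near enough, and the low power at 96 and 64 per arm is real. This stands, and it rules out declaring 58 to 73 the correct requirement.

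A reader might also infer that Section 15 inflates as though whole sites had been randomised. The documents do not support that. No such statement or formula appears, and that design effect would be about 3.1 to 5.2 and would change with children per site.

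It is also fair to say that, if the ICC is between sites, the figures err on the cautious side. Treatment-by-site variation could justify some inflation, but the plan neither invokes it nor gives a figure.

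None of this reconciles the figures. The within-child change factor of 1.55 to 1.60 misses the rows' 1.43 to 1.45, and no single factor gives both the rows and 120.

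**Conclusion.** Wrong as written. On every reading considered, Section 15's required size and its detectable effects cannot both be right: 120 carries a variance factor of 1.67 and the rows 1.43 to 1.45, so for .47 the rows point to about 104 per arm. That result assumes only that one method and the same power and alpha apply throughout, as Section 15 says of power and alpha.

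The correct requirement cannot be settled from the documents. It is about 58 to 73 retained per arm if .20 is between sites, about 111 to 115 for a change contrast if it is within child, and about 70 if that analysis adjusts for baseline. One part is settled by the design: a between-site component should not inflate the size, given household randomisation within shared sites and site in the model.

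Two stronger conclusions are not supported: that the trial was sized as a site-randomised study, and that 96 or 64 retained per arm is shown to be enough for .47. Nor does this point show the trial to be underpowered. The defect lies in the planning figures and leaves the planned analysis intact.

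**What to change.** In Section 15:

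1. State what the ICC of .20 measures (between sites, within child, or a mixture), and whether .47 is in total or within-site SD units.
2. Give the formula, the variance factor and the sidedness of the test.
3. Recompute the required size, the recruitment target and all four detectable effects on that one basis. It should match household randomisation within sites and the Section 5 model, including which contrast is powered, with no inflation for any between-site component. If treatment-by-site variation is meant to be allowed for, say so and give its assumed size.

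The cost is recalculation and rewording of Section 15. Recruitment does not change, because every eligible household is already to be invited.

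### Section 15 needs 120 retained children per arm for d = .47 but says 113 per arm detect the smaller d = .45, at the same 80% power and alpha .05, so its intention-to-treat figures cannot all be right

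*Combined protocol and SAP*

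**What the plan says.** Section 15 (Sample size rationale) bases the intention-to-treat calculation on the 2021 pilot, where the effect on overall child HEI "at the end of the study was .47 with an ICC of .20 for person x site clusters". To detect the same difference between the two randomised arms with 80% power at alpha .05, it states that "we would need to retain 120 children in each arm". It then allows for dropout: "Considering a 15% attrition rate, a target recruitment of approx. 140 children into each active arm".

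Because the club's capacity limits recruitment, the section next gives detectable effects "in two scenarios, maintaining 80% power at" alpha .05, from a pool of about 300 households:

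| Scenario | n per arm | Detectable d |
|---|---|---|
| 75% enrolled | 113 | .45 |
| 75% enrolled, after 15% attrition | 96 | .49 |
| 50% enrolled | 75 | .55 |
| 50% enrolled, after 15% attrition | 64 | .60 |

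No design effect, cluster size, sidedness or formula is given for either set. The ICC of .20 is the only clustering figure, and nothing says that the scenarios rest on a different assumption from the 120.

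**The concern.** With power, alpha and the clustering assumption held fixed, the smallest detectable effect falls as the number per arm rises. If 113 per arm detect .45, then 120 per arm must detect something below .45, and .47 must need fewer than 113. Section 15 says the reverse.

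This is the plan's sample size and power statement for HEI. Either the 120 and the 140 built on it are larger than the plan's own method requires, or the four scenario effects are too optimistic. The second possibility matters more in practice. Recruiting 140 per arm means 280 of about 300 households, or 93%, while the plan models 75% and 50% enrolment. The scenario figures are therefore the ones most likely to describe the trial, and the power they imply at d = .47 depends on which set is right.

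**Working it through.** **Inputs.** All are from section 15: power 80%, alpha .05, and the five pairs (n per arm, d) = (120, .47), (113, .45), (96, .49), (75, .55), (64, .60). Allocation is 1:1 (section 4).

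**Step 1. Try to reproduce the 120.** For a plain two-sided two-sample comparison, n per arm = 2(1.960 + 0.842)² / d² = 15.70 / d². At d = .47 this gives 15.70 / .2209 = 71.1, so 72. The stated 120 therefore carries a variance inflation of about 1.69 that the plan does not state.

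**Step 2. Compare the pairs.** At fixed power, alpha and inflation, n × d² is constant. The range allows d to have been rounded by ±.005. The inflation is n × d² / 15.70.

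| n | d | n × d² | Range | Inflation |
|---|---|---|---|---|
| 120 | .47 | 26.51 | 25.95–27.07 | 1.689 |
| 113 | .45 | 22.88 | 22.38–23.39 | 1.458 |
| 96 | .49 | 23.05 | 22.58–23.52 | 1.468 |
| 75 | .55 | 22.69 | 22.28–23.10 | 1.445 |
| 64 | .60 | 23.04 | 22.66–23.43 | 1.468 |

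The four scenarios agree with one another, with a mean of 22.91 and an inflation of about 1.46. The 120 stands apart, and its range does not overlap theirs.

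**Step 3. Check that the gap does not come from the method.**
- With the t distribution, the inflations are 1.67 against 1.42–1.45.
- One-sided, they are 2.14 against 1.84–1.86.
- With a fixed number of clusters J per arm and ICC .20, the design effect is 1 + (n/J − 1)(.20), so d² = 15.70 × (.80/n + .20/J). This still falls as n rises. Taking J = 11, the site count in section 13, 113 per arm detect .630 and 120 detect .625. The order is the opposite of the one in section 15.

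**Step 4. Consequences if the scenario inflation (about 1.46) is right.**
- n for d = .47: 22.91 / .2209 = 103.7, so 104 retained per arm.
- Recruited at 15% attrition: 104 / .85 = 122.4, so 123 per arm.
- Effect detectable with 120 per arm: √(22.91 / 120) = .437.
- Power at .47 with 120 per arm: Φ(.47 × √(120 / (2 × 1.46)) − 1.96) = Φ(1.05), about 85%.

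**Step 5. Consequences if the inflation behind the 120 (about 1.69) is right.** The detectable effect is .47 × √(120/n), which gives .484, .525, .595 and .644 for n = 113, 96, 75 and 64.

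**Step 6. Power at d = .47 after attrition,** from Φ(.47 × √(n / (2 × inflation)) − 1.96):

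| n per arm | Inflation 1.46 | Inflation 1.69 |
|---|---|---|
| 96 | 77% | 71% |
| 64 | 60% | 53% |

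**Step 7. Check the attrition step.** 120 / .85 = 141.2, which agrees with about 140. The conflict lies in the 120 itself.

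**The case against.** The strongest reply is that little depends on the 120. All eligible households are to be invited whatever the target, and 140 per arm exceeds what either enrolment scenario would deliver. The four scenarios agree, so the simplest reading is that 120 is the odd figure and errs on the safe side. A reader can also already see that neither post-attrition scenario reaches 80% power at .47, because their detectable effects are .49 and .60.

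Much of this stands. Conduct of the trial would not change, and the internal evidence does point to the 120. But agreement among the scenarios shows only that they share an assumption, not that the assumption is correct. Knowing that power is below 80% does not say how far below: the two bases differ by about 6 points at both 96 and 64 per arm.

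A second reply is that the 120 might use the ICC while the scenarios use a different clustering assumption. The constancy of n × d² does require equal inflation, so this is possible. It would still be an undisclosed change of assumption between adjacent paragraphs that are presented as comparable.

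Third, 113 is an enrolled number and 120 a retained one. That does not help, because the plan's own retained 96 detect .49, which places .47 between 96 and 113 per arm.

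**Conclusion.** The inconsistency is real. Under any common set of assumptions, the 120 for d = .47 cannot hold together with the four scenario pairs. It amounts to about 16 children per arm (120 against 104) or, read the other way, about .03 to .04 in each scenario's detectable effect. The conflict itself needs no assumption beyond a common basis for the figures and does not depend on sidedness or on the unstated design effect. The sample sizes and powers above rest on a two-sided normal approximation for two means. The planned analysis in section 5 is a mixed model, so they are planning approximations.

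The documents do not settle which set is in error. If inflation is taken as 1 + (m − 1)(.20), the two sets imply cluster sizes of about 3.3 and 4.5, and neither is stated. The statement should be corrected because it supports the primary comparison, but it does not threaten the design.

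**What to change.** In section 15, state one design effect with its ICC, cluster size and sidedness. Recompute from it the 120, the 140 and the four detectable effects. Add the power at d = .47 for the two post-attrition scenarios (96 and 64 per arm).

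When tracing the 120, check whether attrition entered twice: 104 × 1.15 = 119.6, so the 15% allowance may already be inside the 120 before it is applied again to reach 140. The documents neither confirm nor exclude this. The scenarios multiply by .85 instead, and a target of 85% power at an inflation of 1.45 would also give about 119 (82 × 1.45).

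Justify any inflation kept for site. Households are randomised individually (sections 4 and 13) and both arms attend the same sites (section 11, Arm #2), so a cluster-type inflation of the arm comparison needs a reason.

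The cost is a recalculation and rewording of section 15. Recruitment, design, analysis and data collection are unaffected.
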